9.2.3. Justification of the Clinical Investigation Design

RGnCON is a prospective, comparative, randomized, simple-blinded, monocentric, pilot clinical investigation:

- A **prospective** design has been chosen since no data on the use of RGn550 in sportspeople suffering from acute concussion syndrome were previously collected.
- This investigation is **comparative**. It involves two parallel groups differing in terms of treatment frequency: half of the patients will be treated with 5 Hz, the other half with 10 Hz. This will allow to determine which frequency is optimal for the patient both in terms of safety and performance.
- Patients will be assigned to one of these two groups through **randomization** (1:1 ratio).
- Patients will not be aware of the group they were assigned to (**simple blinded**).
- A **monocentric** design has been chosen because RGnCON is a pilot investigation.

Various methodological aspects will prevent investigation bias:

- The presence of two groups will allow to take into consideration all confounding factors, apart from placebo effect.
- The unpredictable randomization will spread all known and unknown confounding factors (apart from placebo effect) within the two groups, resulting in comparable groups, and will prevent selection bias.

- Patients will be stratified based on gender (male/female) and concussion history (history/no history of concussion within 6 months prior to inclusion) as such parameters are known to influence current concussion symptoms and complications.
- The analysis will be performed in the Full Analysis Set (FAS) population without methods to replace missing data. However, some of the used models take into consideration missing data.

Of note, the following bias will remain present:

- The follow-up bias and evaluation bias since investigators will not be blinded
- The site effect since only one site will be recruited.

Nevertheless, the primary purpose of this investigation is to evaluate, for the first time, the safety of RGn550 in sportspeople suffering from acute concussion syndrome and explore its performance in this population. In case this investigation demonstrates RGn550's safety in this population, further investigation(s), using a double-blinding design versus sham, and involving more sites, will be conducted to demonstrate RGn550's safety and performance.

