9.4. Clinical Investigation Objectives and Hypotheses

As a pilot investigation, the objective of RGnCON is to demonstrate RGn550's safety and explore its performance in treating adult sportspeople with acute concussion syndrome.

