9.5.3. Conduct

9.5.3.1. Patient Inclusion

It is planned to include 50 patients in this investigation (refer to section 9.6.1 for sample size justification).

Based on this number and considering that the site estimated that it would be able to include approximately 3 patients per week, a 4-month inclusion period is planned: from September 2022 to December 2022.

The recruited site will be the Hôpital européen Georges-Pompidou located in Paris. The principal investigator will be a neurologist specialized in sport concussions and the coinvestigator will be a sport physician and posturologist.

In current clinical practice, following a shock, a sportsperson with obvious signs of concussion is examined by a physician within 72 hours after the shock to establish the diagnosis of concussion. For example, in the context of professional rugby, the French federation's regulation requires to follow HIA protocol immediately after the shock and the appearance of such signs. This protocol, composed of three steps, is performed by a physician within 48 hours after the shock:

- Step 1: Assessment during the match using HIA1
- Step 2: Post-match assessment, the same day, using HIA2
- Step 3: 36-48 hours post-injury assessment using HIA3.

The subjects of RGnCON investigation will be identified among sportspersons examined by the principal investigator within 72 hours after the shock. They will be included if they meet eligibility criteria and agree to participate in the investigation. Of note, HIA3 is mentioned in the eligibility criteria as the diagnostic tool for concussion. Indeed, as the principal investigator is the referring neurologist for a lot of rugby clubs and several sports federations, it is expected that most subjects will be professional rugby players for whom this protocol is implemented in current clinical practice. Nevertheless, subjects practicing other sports may be included as well if they have a diagnosis of concussion confirmed by the HIA3, meet the eligibility criteria and agree to participate.

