9.6. Statistical Considerations

9.6.1. Sample Size Justification

For a sample size of 50 patients, the probability of observing at least one ADE will be 0.87 considering a probability of ADE of 0.04. The sample size calculation was performed with SAS® v9.4.

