9.6.3. Statistical Analysis

Full details related to statistical analysis will be provided in the Statistical Analysis Plan.

The statistical analysis will be performed using SAS® Viya v9.4 (or a more recent version).

The global significance level (type I error rate) will be set at $\alpha = 0.05$ (two-sided). Adjustment for multiplicity is not applicable for the primary endpoint and no adjustment for multiplicity is planned for secondary endpoints.

Continuous data will be described by the number of missing data, number of data analyzed, mean, standard deviation, median, Q1, Q3, minimum, maximum.

Categorical data will be described by the number of missing data, frequencies and percentages of patients in each modality. The percentage of patients will be calculated once missing data are excluded from the denominator.

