#### 8.5.1.1. Automated oculomotor and oculopostural functions and balance function

For the evolution of parameters of oculomotor and oculopostural functions and balance function defined in Section 0, the following timepoints will be compared: (D0 after treatment - D0 before treatment, D7 before treatment - D0 before treatment, D7 after treatment - D0 before treatment, and D52 – D0 before treatment). A mixed effect regression model (logistic model for a categorical parameters and a linear model for continuous parameters) will be used with a patient random effect. Group effects (5 Hz vs 10Hz), period effects (D0 before, D0 after, D7 before, D7 after and D52) and the group-by-period interaction will be added as fixed effects. The stratification variable gender (male/female) will be added in the model as covariates.

Note: the stratification variable concussion history within 6 months prior to inclusion (yes/no) will not be added in the model as too few patients had concussion history (cf. data review minutes of 18/07/2023).

The following template will be used for continuous parameters.

	Group of treatment		
Ref = D0 before treatment	RGn550 5Hz N=xx	RGn550 10Hz N=xx	Difference
Endpoint XXX at D0 after treatment			
Adjusted mean	x.xx	x.xx	x.xx
95% CI	x.xx ; x.xx	x.xx ; x.xx	x.xx ; x.xx
p-value	.	.	0.xxx
Endpoint XXX at D7 before treatment			
Adjusted mean	x.xx	x.xx	x.xx
95% CI	x.xx ; x.xx	x.xx ; x.xx	x.xx ; x.xx
p-value	.	.	0.xxx
Endpoint XXX at D7 after treatment			
Adjusted mean	x.xx	x.xx	x.xx
95% CI	x.xx ; x.xx	x.xx ; x.xx	x.xx ; x.xx
p-value	.	.	0.xxx
Endpoint XXX at D52			

		Group of treatment		
Ref = D0 before treatment		RGn550 5Hz N=xx	RGn550 10Hz N=xx	Difference
Adjusted mean		x.xx	x.xx	x.xx
95% CI		x.xx ; x.xx	x.xx ; x.xx	x.xx ; x.xx
p-value		.	.	0.xxx

From an mixed model including treatment (p=0.xxx), visit (p=0.xxx), treatment-by-visit interaction (p=0.xxxx) as fixed effects and variable xxx as random effect, variableyyy (p=0.xxx) as baseline covariate.

The following template will be used for categorical parameters.

	RGn550 10Hz vs RGn550 5Hz at visit 1	RGn550 10Hz vs RGn550 5Hz at visit 2	visit 2 vs visit 1 at RGn550 10Hz	visit 2 vs visit 1 at RGn550 5Hz
Endpoint XXX				
Odds ratio	X.X	X.X	X.X	X.X
95% CI	[X.X ; X.X]	[X.X ; X.X]	[X.X ; X.X]	[X.X ; X.X]

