### 8.5.1.3. Concussion syndrome symptoms (SCAT5)

For concussion syndrome symptoms (SCAT5) functions defined in Section 0, the following timepoints will be analyzed (D0 before treatment, D7 before treatment, D14 and D52), a mixed linear regression model will be used with a patient random effect. Group effects (5 Hz vs 10Hz), period effects and

group-by-period interaction will be added as fixed effects. The stratification variables and SCAT5 baseline will be added in the model as covariates.

The same template as above will be used.

In addition, for exploratory purpose, the concussion syndrome symptoms (SCAT5) will also be analyzed in the subgroup “Number of previous concussions”.

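### Protocol 9.2.3 says the two arms will determine the optimal frequency, but no objective, sample size or deciding contrast in the plan can support that conclusion

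*Protocol*

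**What the plan says.** Protocol 9.2.3 explains why there are two parallel groups: "This will allow to determine which frequency is optimal for the patient both in terms of safety and performance". The section ends by describing the main purpose as a first safety evaluation with exploration of performance, and leaves demonstration to later double-blind sham-controlled work. Protocol 9.4 likewise says the aim is to "explore its performance in treating adult sportspeople with acute concussion syndrome".

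The objectives in 9.4.1 and 9.4.2 mention both frequencies but do not compare them. The sample size (9.6.1) is justified by one statement: "the probability of observing at least one ADE will be 0.87 considering a probability of ADE of 0.04". On size and allocation, "It is planned to include 50 patients in this investigation" (9.5.3.1) and "Patients will be assigned to one of these two groups through randomization (1:1 ratio") (9.2.3), so about 25 per arm.

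The performance endpoints (Protocol 9.5.4.2, SAP 6.2.2) form an unranked list. For oculomotor and balance measures, SAP 8.5.1.1 states that "the following timepoints will be compared: (D0 after treatment - D0 before treatment" and three further changes from baseline. For SCAT5, SAP 8.5.1.3 states that "the following timepoints will be analyzed (D0 before treatment, D7 before treatment, D14 and D52"). The models contain group and group-by-period terms. The template for continuous parameters prints a between-arm difference, 95% CI and p-value at each time point; the template for categorical parameters prints odds ratios with 95% CIs. Protocol 9.6.3 adds that "no adjustment for multiplicity is planned for secondary endpoints", and SAP 7.2 makes no alpha adjustment either.

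**The concern.** To determine an optimum is to select. That needs a rule for what makes one frequency better, and enough information to apply it. Neither document names a deciding endpoint, time point, margin or hierarchy, and the list of changes in SAP section 10 adds none. The selection sentence also sits badly beside the exploratory wording in the same section: both cannot describe the same comparisons.

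What is at stake is what the report may conclude. With many unranked between-arm results and a protocol that promises an optimum, a report could cite any favourable contrast as fulfilling a stated purpose of the design. The safety half of the sentence has no rule either: ADE proportions are given by group with exact intervals, and no between-arm comparison is planned.

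**Working it through.** **1. The plan's own figure.** Inputs: 50 patients and ADE probability 0.04 (Protocol 9.6.1). P(at least one ADE) = 1 − 0.96^50 = 0.870, which reproduces the stated 0.87. It is a detection probability for both arms pooled. For one arm of 25 it is 1 − 0.96^25 = 0.64. Neither figure concerns a difference between frequencies.

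**2. Count of between-arm contrasts** (SAP 6.2.2 and 8.5.1.1 to 8.5.1.3).

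| Measure | Contrasts |
|---|---|
| NPC, 4 times | 4 |
| Statokinesigram area, eyes open and closed, 4 times | 8 |
| TMT A and B, time and errors, 1 change each | 4 |
| SCAT5, 2 scores, 3 post-baseline times | 6 |
| **Core** | **22** |
| TMT B−A, time and errors | 2 |
| Romberg quotient, 4 times | 4 |
| SKDI, eyes open and closed (assumed), 4 times | 8 |
| Left distribution, eyes open and closed, 4 times | 8 |
| **With derived measures and left percentage** | **44** |
| Cover test and three Maddox endpoints, 4 times each | 16 |
| **All** | **60** |

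Right distribution is omitted because it is the complement of left. Blood markers (descriptive only), subgroups and the pooled D0 to D52 analysis are not counted. The core is the fairer figure. B−A, Romberg and SKDI are computed from other listed measures, and a raw left percentage has no better direction, since Protocol 9.5.5.1 treats 50% on each foot as stable.

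**3. Chance of at least one significant contrast if the frequencies are equal.** The documents give no correlations, so a common correlation ρ between two-sided 0.05 z-tests is assumed:

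P = 1 − ∫ [Φ((1.96 − √ρ·x)/√(1−ρ)) − Φ((−1.96 − √ρ·x)/√(1−ρ))]^k φ(x) dx

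At ρ = 0 this is 1 − 0.95^k: 1 − 0.95^22 = 0.68 and 1 − 0.95^60 = 0.95.

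| k | ρ = 0 | ρ = 0.5 | ρ = 0.8 |
|---|---|---|---|
| 22 | 0.68 | 0.44 | 0.23 |
| 60 | 0.95 | 0.66 | 0.31 |

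One contrast named in advance gives 0.05.

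**4. What one contrast can detect.** With 25 per arm and two-sided 0.05, the difference detectable with 80% power is (1.960 + 0.842) × √(2/25) = 0.79 SD. At 0.5 SD the power is about 42%. These effect sizes are assumptions, because the plan gives no effect size, SD or margin for any performance endpoint.

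**5. Significant results in opposite directions.** For 60 contrasts and no true difference, the chance of at least one in each direction is 0.61 at ρ = 0, 0.11 at ρ = 0.3 and 0.01 at ρ = 0.5.

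**The case against.** The strongest reply is that this is one loose sentence in a rationale. It is not an objective, hypothesis or decision procedure, and the exploratory status is stated in the same section and again in 9.4. The lack of multiplicity adjustment is disclosed and acceptable in a pilot. The chances in step 3 assume equal frequencies, in which case choosing either one does no harm to performance. The categorical template prints no p-value per contrast.

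Most of this stands, and it limits the weight of the point. It does not rescue the sentence: if the comparisons are exploratory, the promise to determine an optimum is wrong as written. The step 3 figures show how easily an apparent winner arises. They are not an objection to unadjusted alpha, and they do not measure the risk of choosing the worse frequency.

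A reader might infer three stronger things that the documents do not support:

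- **That statistical significance will pick the winner.** Neither document says so; both are silent on any rule.
- **That the winning frequency will be carried into the later sham-controlled trials.** Protocol 9.2.3 makes those trials conditional on safety and does not mention frequency.
- **That the tables are likely to point both ways at once.** At a correlation of 0.5 the chance of opposing significant results is only about 0.01. The high figure needs independence, which is implausible for repeated and derived measures on the same patients.

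**Conclusion.** The point holds as an overclaim that conflicts with the plan's own wording. Protocol 9.2.3 attributes to the design an ability it does not have, for safety or for performance. With no true difference, the chance of at least one nominally significant between-arm contrast is about 0.44 (22 contrasts) to 0.66 (60 contrasts) at an assumed correlation of 0.5. Over correlations from 0.8 to 0 it runs from 0.23 to 0.68 and from 0.31 to 0.95. The figures rest on those assumed correlations and on the counting choices shown. The power limit of about 0.8 SD assumes 25 evaluable patients per arm. The primary endpoint, its analysis and the data collected are unaffected.

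**What to change.** In Protocol 9.2.3, replace the sentence on the optimal frequency with: *The 5 Hz vs 10 Hz comparisons are exploratory; they may inform later investigations but will not by themselves identify an optimal frequency.* Add the same statement to SAP 8.5.1, which at present says nothing on the matter, and to the clinical investigation report. This needs no new data and no new model. The small downside is a weaker claim about frequency selection.

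Naming one deciding contrast is optional and involves a trade-off. It would have to be fixed before any by-group results are seen. That matters here because investigators are unblinded and SAP version 2.0 (03/08/2023) follows the data review of 18/07/2023. The contrast would still be underpowered for moderate differences. The time point also needs thought: SCAT5 at D14, for example, falls about when Protocol 9.2.1.1.3 expects adult symptoms to have resolved (10 to 14 days), so there may be little left to separate the arms.

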9.2.1.1.3. Symptoms

In the acute phase, concussion is an evolving injury with rapidly changing clinical signs and symptoms [2].

These symptoms can be categorized into [1–3, 6, 7]:

- Somatic symptoms, such as:
 - Headache
 - Vision changes including blurred vision, light sensitivity, difficulty reading and convergence dysfunction
 - Coordination disorders
 - Disturbance in balance
 - Insomnia
 - Somnolence
 - Drowsiness

| | | |
|--------|---|--|
| RGnCON | Clinical Investigation Plan Version 2.0 - 11 August 2022 | |
|--------|---|--|

- Cognitive impairment, such as:
 - Feeling like in a fog
 - Disorientation
 - Difficulty concentrating
 - Slowed reaction time
 - Loss of consciousness
 - Amnesia
 - Neurological deficit
- Emotional / behavioral changes such as:
 - Irritability
 - Lability

Altogether, this set of symptoms is called **concussion syndrome** [1, 6].

In adults, symptoms typically resolve in 10 to 14 days [2]. However, some may linger for weeks. Persistent post-concussion syndrome occurs when symptoms persist beyond 3 months [6].

Of note, well-trained and well-prepared sportspersons are thought to heal more rapidly [1, 4].

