9.2.1.1.4. Complications

Although the short-term vital prognosis is very good (mortality < 1%), the functional prognosis in the mid- and long-term is more uncertain. Indeed, approximately 10-20% of the patients will have long-lasting effects [3].

The literature on neurobehavioral sequelae and long-term consequences of exposure to recurrent head trauma is inconsistent. However, reported potential long-term problems include [1, 2]:

- Cognitive impairment
- Depression
- Chronic traumatic encephalopathy (although a cause-and-effect relationship has not yet been demonstrated between chronic traumatic encephalopathy and concussion).

Of note, well-trained and well-prepared sportsperson are thought to have less complications. Interestingly, concussions have been reported to be more severe in sportswomen than sportsmen [1].

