9.4.2. Secondary Objectives

The secondary objectives of this investigation relate to both the **safety** and **performance** of RGn550 in acute concussion syndrome, when used to deliver, either at a frequency of 5 Hz or 10 Hz, two 20-min treatment sessions at 1 week apart.

These objectives are:

- To evaluate the **incidence of RGn550's ADEs per severity, AEs and Device Deficiencies (DDs)**
- To evaluate the effect of RGn550, after the first and second treatment sessions and then 45 days after the second treatment session, on:
 - **Automated oculomotor and oculopostural functions**
 - **Balance function**
 - **Executive function**
- To assess the effect of RGn550 on **concussion syndrome symptoms** 7 days after the first treatment session as well as 7 and 45 days after the second treatment session.
- To evaluate the effect of RGn550 on **blood markers** that are involved in the pathogenesis of concussion 45 days after the second treatment session.

These secondary objectives have been chosen as they will allow to evaluate RGn550's safety and determine whether:

- RGn550 could improve important functions that are impacted in acute concussion syndrome, i.e., automated oculomotor/oculopostural, balance and executive functions
- RGn550 could decrease acute concussion syndrome symptoms
- RGn550 could impact the concentration of blood markers involved in acute concussion syndrome

| | | |
|--------|---|---|
| RGnCON | Clinical Investigation Plan Version 2.0 - 11 August 2022 |  |
|--------|---|---|

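### The two arms control confounding for 5 Hz versus 10 Hz, but not for the effect of RGn550 that the performance objectives ask about

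*Protocol*

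**What the plan says.** **Design.** Protocol 9.2.3 sets up two arms: "half of the patients will be treated with 5 Hz, the other half with 10 Hz". There is no sham, untreated or usual-care group. The stated reason for two arms is to find the better frequency. Among the features said to prevent bias is: "The presence of two groups will allow to take into consideration all confounding factors, apart from placebo effect". The biases listed as remaining are follow-up and evaluation bias from unblinded investigators, and the single-site effect. The section closes by saying that the study evaluates safety and explores performance, and that later sham-controlled work is to demonstrate both.

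**Objectives.** Protocol 9.4.2 frames the performance question differently: "To evaluate the effect of RGn550, after the first and second treatment sessions and then 45 days after the second treatment session, on" oculomotor, balance and executive function. The aim is to learn whether "RGn550 could improve important functions that are impacted in acute concussion syndrome", with parallel aims for symptoms and blood markers. The synopsis carries the same objectives, and 9.3.1 says these potential benefits are studied in this trial.

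**Natural course.** Protocol 9.2.1.1.3 puts usual symptom resolution in adults at 10 to 14 days.

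**Analysis.** Protocol 9.6.3.2 and SAP 8.5.1.1 to 8.5.1.3 use mixed models with group, period and their interaction. The SAP template for categorical parameters also reports visit-to-visit odds ratios within each arm, and SAP 8.5.1.4 describes marker change from baseline. The note closing SAP 8.5.1.3 adds a second model on all patients, comparing D0 with D52, with a patient random effect and period as the only fixed effect.

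**The concern.** The objective and the randomised contrast do not match. The objective concerns RGn550 against no RGn550; the contrast is RGn550 at one frequency against RGn550 at another. Anything common to both arms drops out of the contrast and stays in full in every change from baseline. In a condition that usually resolves on its own during follow-up, that common part may be large.

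A reader who applies the 9.2.3 sentence to the 9.4.2 objectives would conclude that only placebo response stands between an observed improvement and a device effect. The pooled D0 to D52 model then supplies a significance test for exactly that improvement. Protocol 9.2.1.2.1 criticises earlier photobiomodulation studies for lacking control and randomisation. For the effect of the device, as distinct from frequency, this trial has no control either.

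**Working it through.** **1. The plan's own figure.** Protocol 9.6.1 gives a probability of 0.87 of seeing at least one ADE with 50 patients and an ADE probability of 0.04. Check: 1 − 0.96^50 = 0.8701. It reproduces and is not in dispute. It is the only sample-size basis; no effect size, SD or power is given for any performance parameter.

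**2. What each analysis estimates.** Write the expected change from D0 at time t in arm j as

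C_j(t) = R(t) + L(t) + M(t) + P(t) + E_j(t),

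where R is spontaneous recovery, L test repetition, M regression to the mean, P placebo response and E_j the device effect at frequency j. Randomisation, with patients blinded, makes the first four equal in expectation across arms.

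- Between arms: C_10 − C_5 = E_10 − E_5. The shared terms cancel, placebo included.
- Pooled, 1:1: (C_10 + C_5)/2 = R + L + M + P + (E_10 + E_5)/2. Nothing cancels.

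Neither expression isolates E_5 or E_10.

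**3. Timing.** D0 falls within 72 h (3 days) of the shock, so D7 is 7 to 10 days after it, D14 is 14 to 17 days after it, and D52 is 52 to 55 days after it. Set against 10 to 14 days, D7 lies within the usual recovery period and D14 and D52 at or beyond its end. The same-day comparisons around a 20-minute session are different: R is close to zero there, although L, P and the unblinded assessor remain.

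**4. Between-arm test.** Inputs: 25 per arm (50 patients, 1:1) and two-sided 5% from the plan; effects in SD of the change score are my assumptions. For a difference of 0.5 SD the noncentrality is 0.5 × √(25/2) = 1.77.

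| True situation | P(significant) |
|---|---|
| Neither frequency works | 5% |
| Both help by 0.5 SD | 5% |
| One helps by 0.5 SD, the other does nothing | 41% |
| One harms by 0.5 SD, the other does nothing | 41% |

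The first two rows cannot be told apart, nor can the last two. Precision is limited as well: the difference detectable with 80% power is (1.960 + 0.842) × √(2/25) = 0.79 SD (0.81 by the t distribution), and the 95% CI half-width is 2.011 × √(2/25) = 0.57 SD. A non-significant result would therefore not show that the frequencies are equal.

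**5. Pooled D0 to D52 test with an inert device.** For a continuous parameter seen at both visits, a random-intercept model with period alone amounts to a paired t test (SAP 8.4.1 reports 0% loss to follow-up at data review). With N = 50 and mean natural recovery r in SD of the change score, the noncentrality is r√50.

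| Assumed r | r√50 | P(significant) |
|---|---|---|
| 0.2 | 1.41 | 28% |
| 0.3 | 2.12 | 55% |
| 0.5 | 3.54 | 93% |
| 0.8 | 5.66 | about 100% |

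The pooled test can also hide harm. With r = 1.0, one setting harmful by 0.5 SD and the other inert, the mean change is still 0.75 SD towards improvement, and the test was significant in 99.9% of 20,000 simulated trials.

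**The case against.** The strongest reply is context. In 9.2.3 the sentence follows the statement that two arms serve to find the better frequency, and precedes the point about randomisation producing comparable groups. Read that way it describes the 5 Hz versus 10 Hz comparison and is broadly right. This stands for that comparison. But the exception made for placebo fits poorly there, because placebo response is shared by two patient-blinded arms and largely cancels. It fits the question of device against nothing, and for that question the other shared influences needed the same exception.

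The limits are also partly disclosed: a pilot, safety primary, performance to be explored, demonstration left to a sham-controlled study. This stands too, and it makes the point one of wording and interpretation. A two-setting pilot without sham is a legitimate choice. The disclosure still never names natural recovery, and it does not cover the pooled model that the SAP added.

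A reader might go further and infer from the statement that "approximately 10-20% of the patients will have long-lasting effects" that 80 to 90% of patients would have recovered by D52 with an inert device, and take that as the size of the bias. The documents do not support this. The statement concerns mid- and long-term function and is not tied to D52, and 9.2.1.1.3 places persistent syndrome beyond 3 months. Freedom from long-lasting effects is not the same as improvement in convergence, deviation, balance, TMT or cytokines. No planned analysis counts patients improved.

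**Conclusion.** The concern holds for the effect of RGn550 and not for the comparison of frequencies. For the 9.4.2 objectives, the claim in 9.2.3 gives the design a property that it lacks, and the list of remaining biases omits the most obvious threat, natural recovery, along with test repetition and regression to the mean. The exposure is clearest at D7, D14 and D52 and smaller for same-day changes.

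The size depends on how much patients recover unaided, which the documents do not quantify on any measured parameter. Under assumed recovery of 0.2 to 0.8 SD of the change score, the pooled model would give a significant change with an inert device in 28% to about 100% of trials, per continuous parameter, at two-sided 5% with 50 complete pairs.

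A reader might also infer that the between-arm result says nothing about the device. That is too strong: a real difference would show that frequency matters, so at least one setting has some effect. It would not show that either setting improves on natural recovery. The primary ADE analysis is not touched by this point.

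**What to change.** 1. **Protocol 9.2.3.** Limit the sentence, for example: *Two randomised groups control confounding for the comparison of 5 Hz with 10 Hz only. Because both groups are treated, spontaneous recovery, test-repetition effects, regression to the mean and placebo effect are not controlled for the effect of RGn550 itself.* Add these four to the remaining biases for the effect of RGn550.
2. **Protocol 9.4.2 and synopsis.** Restate the performance objectives as (a) comparing 5 Hz with 10 Hz and (b) describing the course of each parameter in treated patients.
3. **SAP 8.5.1.1 to 8.5.1.4 and the note closing 8.5.1.3.** Add: *Changes from D0 within an arm or in all patients are descriptive and are not attributed to RGn550. Absence of a difference between frequencies is not evidence for or against an effect of RGn550; that question is left to the announced sham-controlled investigation.* List the pooled model in SAP section 10, which does not mention it.

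If the protocol can no longer be amended, the same statements belong in the clinical investigation report. No extra patients or data are needed, and no planned estimate changes. The price is a more modest stated performance objective.
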